13.3 Safety Measurements

- Adverse events by severity and causality as described in section 7.7
- Laboratory evaluations including SMA-21 and CBC with differentials.
- Clinically meaningful changes in vital signs including temperature, blood pressure, weight, pulse, and respiratory rate

13.4 Pharmacokinetic and Bioanalytical Methods

No pharmacokinetics will be performed.

13.5 Treatment Requirements

Subjects must complete at least 1 treatment and have a follow up visit at 21 days (± 7 days) to be evaluated for efficacy.

13.6 Timing of the Therapeutic Dose

Therapy will be administered every 21 days (± 7 days) for up to three applications or until there is complete closure of the perforation. A cross over will occur if the perforation is

not completely closed at Visit 4. A Final Visit will occur in 2 months (+ 7 days) following the subject's last appointment.

14. Study Conduct

14.1 Visit 0, Screening

The following procedures will be performed:

- Administration of Informed Consent Form
- Review of inclusion and exclusion criteria
- Medical history of the Tympanic Membrane
- Otologic Exam
- Vital Signs
- Laboratory evaluation (hematology and chemistry): *CBC, Basic Metabolic Panel Test, HbA1c*
- Pregnancy Test if applicable
- Review of Prior/ Concomitant medication(s)
- Optional: Study drug administration (if all eligibility requirements can be confirmed at this visit)
- Optional: TM photography
- Optional: Audiogram

14.2 Visit 1, Day 1, IMP Administration

The following procedures will be performed:

- Review of inclusion and exclusion criteria
- Vital Signs
- Review of Prior/ Concomitant medication(s)
- TM photography- *if not done at the time of screening*
- Audiogram- *if not done at the time of screening*
- Study Drug Administration- *if not done at the time of screening*
- Assessment of Possible Adverse events

14.3 Visit 2, Day 22 (\pm 7 Days)

The following procedures will be performed:

- Study drug administration - *if the TMP is not completely closed*
- Vital Signs
- Review of Prior/ Concomitant medication(s)
- TM photography
- Audiogram
- Assessment of Possible Adverse events

14.3 Visit 3, Day 43 (\pm 7 Days)

The following procedures will be performed:

- Study drug administration- *if the TMP is not completely closed*

- Vital Signs
- Review of Prior/ Concomitant medication(s)
- TM photography
- Audiogram
- Assessment of Possible Adverse events

14.4 Visit 4, 64 days after the first treatment (± 7 Days)

The following procedures will be performed:

- Study Drug administration- *If the TMP is not completely closed, then the blind on the subject's randomization status will be broken. Placebo subjects will be crossed over to FGF-2 treatment arm at this visit.*
- Vital Signs
- Review of Prior/ Concomitant medication(s)
- TM photography
- Audiogram
- Assessment of Possible Adverse events

14.5 Visit 5, 85 days after first treatment (± 7 Days)

This is a follow up visit for all subjects who were crossed over to the other treatment group at Visit 4. The following procedures will be performed:

- Study Drug administration- *if the TMP is not completely closed*
- Vital Signs
- Review of Prior/ Concomitant medication(s)
- TM photography
- Audiogram
- Assessment of Possible Adverse events

14.6 Visit 6, 106 days after first treatment (± 7 Days)

This is a follow up visit for all subjects who were crossed over to the other treatment group at Visit 4. The following procedures will be performed:

- Study Drug administration- *if the TMP is not completely closed*
- Vital Signs
- Review of Prior/ Concomitant medication(s)
- TM photography
- Audiogram
- Assessment of Possible Adverse events

14.7 Visit 7, 127 days after first treatment (± 7 Days)

This is a follow up visit for all subjects who were crossed over to the other treatment group at Visit 4. No treatment medication will be given. The following procedures will be performed:

- Vital Signs
- Review of Prior/ Concomitant medication(s)
- TM photography
- Audiogram

- Assessment of Possible Adverse events

14.8 Final Visit (2 Months Following Last Appointment, \pm 7 Days)

In order to complete the study, a final follow up visit will be completed. The following procedures will be performed:

- Otolgic Exam
- Vital Signs
- Laboratory evaluation (hematology and chemistry): *CBC, Basic Metabolic Panel Test, HbA1c*
- Review of Prior/ Concomitant medication(s)
- TM photography
- Audiogram
- Tympanometry
- Assessment of Possible Adverse events

15. Primary Safety and Efficacy Variable(s)

15.1 Adverse Events (AE)

An Adverse Event will be considered any unfavorable or unintended change in structure, function, signs, or symptoms temporally associated with the use of a medicinal product experienced by a person administered a pharmaceutical product, whether or not a causal relationship with the product has been established. Clinically significant laboratory abnormalities may be considered AEs if deemed appropriate by the Investigator. Worsening of a pre-existing condition is also considered an AE as is the discovery of an abnormal finding during physical exam that was not included in the medical history.

Subjects will be encouraged to spontaneously report any AE. Study personnel will ask open-ended questions to obtain information about AEs at every visit. Date and time of onset and resolution (if applicable) of the AE will be documented.

15.2 Causality

Events will be considered drug related if classified by the Investigator as possible, probable, or definite. Association of events to the study drug will be made using the following definitions:

Term	Definition
Definitely Not	The event is definitely not associated with study medication.
Probably Not	The temporal association, patient history, or clinical condition is such that the study medication is not likely to have had an association with the observed event.
Possible	The event: a) follows a reasonable temporal association with the study medication administration, but b) could have been produced by the patient's clinical condition or other therapy.
Probable	The event: a) follows a reasonable temporal association with the study medication, b) abates upon discontinuation of study medication, and c) can't be reasonably explained by the patient's clinical condition or other therapy.
Definite	The event: a) follows a reasonable temporal association with the study medication, b) abates upon discontinuation of study medication, c) cannot be reasonably explained by the patient's clinical condition or other therapy, and d) reappears on re-exposure to the study medication.
Unknown	Not enough information exists for the assessment of causality at the time of occurrence.

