15.4 Serious Adverse Event (SAE)

A Serious Adverse Event is an AE that:

- Is fatal
- Is life-threatening, meaning the subject was, in the view of the Investigator, at immediate risk of death from the reaction as it occurred, i.e., it does not include a reaction that, had it occurred in a more serious form or progressed, might have caused death
- Is a persistent or significant disability or incapacity
- Requires or prolongs inpatient hospitalization. [Inpatient hospitalization will be considered a hospitalization that is longer than 24 hours, or a hospitalization that requires an intervention to treat emergent symptomatology (non-diagnostic)]
- Is a congenital anomaly or birth defect.

Other important medical events may be considered SAEs when, based upon appropriate medical judgment, they may jeopardize the subject and may require medical or surgical intervention to prevent one of the outcomes as listed (# 1-5 above) in this definition.

All SAEs, including death, due to any cause that occurs during this study and until 30 days after the last dose of study medication, whether or not expected and regardless of causality, must be reported to the Medical Monitor immediately upon discovery of the event, using an SAE Form, by fax and, if necessary, by phone.

The Medical Monitor will advise the Investigator regarding the nature of any further information or documentation that is required. The Investigator should provide the following documentation at the time of notification if available:

- SAE Form
- AE (CRF) page
- Concomitant and support medication pages
- Relevant diagnostic reports
- Relevant laboratory reports
- Admission notes
- Hospital discharge summary (when available).

Nobelpharma will make available to the Investigator any reports of serious, unexpected, and drug-related AEs by fax within eight (8) days of notification of the event using a *MedWatch 3500A Form*. The Investigator must promptly (within 2 days) inform the IRB of such events and retain a copy of the notification in the site's Regulatory Binder.

All SAEs must be followed until the event resolves, returns to baseline or, in the opinion of the Investigator, becomes stable. Hospitalization of subjects for the administration of chemotherapy will not be considered an SAE.

16. Data Quality Assurance

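### Section 15.2 has no drug-related category for an event that follows study drug, has no other reasonable explanation and does not abate

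*Combined protocol and SAP*

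**What the plan says.** Section 15.2 gives six causality ratings and counts three of them as drug related: "Events will be considered drug related if classified by the Investigator as possible, probable, or definite". All three require a reasonable temporal association. They also require the following.

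- **Possible:** the event "could have been produced by the patient's clinical condition or other therapy".
- **Probable:** the event "abates upon discontinuation of study medication", and the patient's condition or other therapy cannot reasonably explain it.
- **Definite:** everything in Probable, plus "d) reappears on re-exposure to the study medication".

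Definitely Not, Probably Not and Unknown are outside the drug-related list. Unknown is defined as "Not enough information exists for the assessment of causality at the time of occurrence", and 15.2 has no rule for revisiting that rating.

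The label is used in two places. Under 15.4 the sponsor sends investigators "any reports of serious, unexpected, and drug-related AEs by fax within eight (8) days of notification of the event", and the investigator must then inform the IRB within 2 days. Section 20 summarises adverse events by attribution within body system. When a subject has the same event more than once, it uses the rating nearest to drug related. It does not say where Unknown ranks.

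**The concern.** The ordering of the scale is inverted for lasting harm. Take permanent sensorineural hearing loss after FGF-2 with nothing else to account for it. Because no rival cause exists, it fails Possible. Because it is permanent, it fails Probable and Definite. If a rival cause did exist, the same event would be Possible and would count. Removing the competing explanation strengthens the case against the drug but takes the event out of the related group.

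The same holds for serious outcomes that 15.4 itself lists, such as death or persistent disability, which by nature do not abate.

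At stake are the expedited report and IRB notice that depend on the label, and the attribution summaries. Section 18 also has attribution recorded as part of safety monitoring.

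**Working it through.** No figure in the plan is in dispute, so the check is an enumeration of the 15.2 definitions as written.

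**Inputs.** Temporal association is fixed at yes. Three criteria then vary:

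- other explanation: yes or no
- abates on discontinuation: yes or no
- re-exposure: event reappears, does not reappear, or no re-exposure took place

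This gives 2 × 2 × 3 = 12 profiles.

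**Rules applied.**

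- Possible = other explanation
- Probable = no other explanation AND abates
- Definite = Probable AND reappears on re-exposure

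| Other explanation | Abates | Profiles | Related category available |
|---|---|---|---|
| Yes | Yes | 3 | Possible |
| Yes | No | 3 | Possible |
| No | Yes | 3 | Probable (1 of the 3 also Definite) |
| No | No | 3 | None |

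So 3 + 3 + 3 = 9 profiles have a related category and 12 − 9 = 3 do not, whatever the re-exposure result. These 3 are combinations of criteria. They say nothing about how often such events occur.

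**What is left for those 3.** The two Not ratings contradict the facts of the case. Unknown is the nearest remaining rating but fits poorly, because it is meant for missing information and here the facts may be complete. On either choice the event is not counted as drug related.

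**Fit with the dosing design.** Section 13.6 has treatment applied every 21 days (± 7 days), up to three times, on a bioabsorbable sponge. There is no continuous exposure to withdraw, so abatement on discontinuation is hard to judge, and more so after the last application. The synopsis and Section 7.3 both withhold further treatment after an ear complication, so re-exposure, and with it Definite, is largely out of reach for ear harm. The two places differ on whether this applies when the first treatment or when three treatments have not closed the perforation. They must be reconciled, but the gap in 15.2 does not depend on which is meant.

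**Recount with condition (b) of Probable widened to irreversible events or events whose dechallenge cannot be assessed.** The 3 open profiles become Probable whenever either reason explains the lack of abatement. All 12 then have a related category: 6 Possible and 6 Probable, of which 1 also meets Definite under its unchanged conditions.

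**The case against.** The strongest case against is that the gap is narrow and the event is not lost.

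- **Most ear harms already count.** Possible needs only that something else could have caused the event. Section 2 lists sensorineural loss as a rare complication of middle-ear infection and describes epithelial ingrowth through a perforation. Each application also involves topical lidocaine, roughening of the perforation edge and fibrin glue. A rival cause will often be available. This stands, and it limits the point to events with no reasonable other explanation.
- **Other channels do not use the label.** Section 15.4 sends SAEs to the Medical Monitor regardless of causality, during the study and until 30 days after the last dose. Section 18 brings all unexpected or serious events to the DSMB. Section 19 has the Research Monitor report independently on unanticipated problems. Section 20 reports all treatment-emergent events and summarises SAE incidence by arm, with narratives for serious events. This also stands.
- **An investigator might stretch Possible to cover the event.** That departs from the definition, and the two sites named in Section 26 could do it differently. It does not repair the text.

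A reader might infer more than the documents support:

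- **That permanent harm probably due to FGF-2 generally drops out of safety reporting.** The first two items above show otherwise.
- **That Unknown is treated as unrelated.** It is a separate rating from both Not categories, and its wording suggests a provisional one. It is only not counted as related.
- **That one or two misrated events would empty a table of drug-related serious events.** Section 20 lists attribution and serious incidence separately and specifies no such table.
- **That the 18% cholesteatoma figure in Section 3.1 indicates the size of the problem.** It concerns a different growth factor in an animal model.

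**Conclusion.** The point holds in a limited form. Read literally, 15.2 cannot class as drug related an event that follows study drug, has no reasonable other explanation and does not abate. That event misses the 15.4 report and IRB notice (if serious and unexpected) and the related rows of the Section 20 attribution tables. Neither the primary efficacy result nor the all-cause safety comparison by arm is affected.

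The size cannot be stated as a rate, because the documents give no frequency for such events. For scale only, one event among the 45 FGF-2 patients in the synopsis sample-size statement is 1/45 = 2.2% of that arm.

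The conclusion assumes that investigators apply the definitions as written and that some lasting events will have no plausible other cause. It is a wording defect that gives an inverted result and is worth correcting because the correction costs so little.

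**What to change.** **Main change, Section 15.2.** In Probable, extend condition (b) so that it is also met when the event is irreversible or when dechallenge cannot be assessed. Leave Definite as it is. Relaxing its re-exposure condition where re-treatment was withheld would merge it with Probable for ear events, and nothing would be gained since both already count as related.

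**Secondary change.** State that events rated Unknown are handled as drug related for 15.4 reporting and for the Section 20 attribution tables until they are reclassified. This also settles where Unknown ranks.

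**Cost.** Two short pieces of protocol wording and a CRF completion note, with no effect on dosing, visits or sample size. The downside is that a few more events will be labelled drug related.

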15.3 Severity

Signs and symptoms will be graded by the Investigator using the NCI Common Toxicity Criteria and graded as mild, moderate, severe, or life-threatening according to the following definitions:

Grade	Definition
Mild	Causing no limitation of usual activity

Grade	Definition
Moderate	Causing some limitations of usual activities
Severe	Causing inability to carry out usual activities
Life-Threatening	Subject was at immediate risk of death from the event

15.4 Serious Adverse Event (SAE)

A Serious Adverse Event is an AE that:

- Is fatal
- Is life-threatening, meaning the subject was, in the view of the Investigator, at immediate risk of death from the reaction as it occurred, i.e., it does not include a reaction that, had it occurred in a more serious form or progressed, might have caused death
- Is a persistent or significant disability or incapacity
- Requires or prolongs inpatient hospitalization. [Inpatient hospitalization will be considered a hospitalization that is longer than 24 hours, or a hospitalization that requires an intervention to treat emergent symptomatology (non-diagnostic)]
- Is a congenital anomaly or birth defect.

Other important medical events may be considered SAEs when, based upon appropriate medical judgment, they may jeopardize the subject and may require medical or surgical intervention to prevent one of the outcomes as listed (# 1-5 above) in this definition.

All SAEs, including death, due to any cause that occurs during this study and until 30 days after the last dose of study medication, whether or not expected and regardless of causality, must be reported to the Medical Monitor immediately upon discovery of the event, using an SAE Form, by fax and, if necessary, by phone.

The Medical Monitor will advise the Investigator regarding the nature of any further information or documentation that is required. The Investigator should provide the following documentation at the time of notification if available:

- SAE Form
- AE (CRF) page
- Concomitant and support medication pages
- Relevant diagnostic reports
- Relevant laboratory reports
- Admission notes
- Hospital discharge summary (when available).

Nobelpharma will make available to the Investigator any reports of serious, unexpected, and drug-related AEs by fax within eight (8) days of notification of the event using a *MedWatch 3500A Form*. The Investigator must promptly (within 2 days) inform the IRB of such events and retain a copy of the notification in the site's Regulatory Binder.

All SAEs must be followed until the event resolves, returns to baseline or, in the opinion of the Investigator, becomes stable. Hospitalization of subjects for the administration of chemotherapy will not be considered an SAE.

16. Data Quality Assurance

16.1 Source Data and Records

Source data are all the information in original records and certified copies of original records of clinical findings, observations, laboratory reports, data sheets provided by the sponsor or other activities in the study, which are necessary for the reconstruction and evaluation of the study. The investigator will permit study-related monitoring, audit(s), IRB review(s) and regulatory inspection(s), with direct access to all the required source records.

In the event the Investigator retires, relocates or for any other reason withdraws from the responsibility for maintaining records for the period of time required, custody of the records may be transferred to any other person who will accept responsibility for the records. Notice of such a transfer must be given in writing to the Sponsor. The Investigator must contact the Sponsor prior to disposal of any records related to this study.

16.2 Reporting of Results

The Case Report Form (CRF) is an integral part of the study and subsequent reports. The CRF must be used to capture all study data recorded in the subject's medical record. The CRF must be kept current to reflect subject status during the course of the study. Only a Subject screening and randomization number and subject initials will be used to identify the Subject.

The principal investigator and/or study coordinator is responsible for performing on-site monitoring at regular intervals throughout the study to verify adherence to the protocol; verify adherence to local regulations on the conduct of clinical research; and ensure completeness, accuracy, and consistency of the data entered in the CRF.

The Data Safety and Monitoring Committee and the principal investigator will monitor completed Case Report Forms (CRFs). A case report form will be provided for each screened subject.

All protocol-required information collected during the study must be entered by the Investigator, or designated representative, in the CRF. All details of the CRF completion and correction will be explained to the investigator.

If the Investigator authorizes other persons to make entries in the CRF, the names, positions, and signatures of these persons must be supplied to the sponsor.

The Investigator, or designated representative, should complete the CRF as soon as possible after information is collected, preferably on the same day that a study Subject is seen for an examination, treatment, or any other study procedure. Any outstanding entries must be completed immediately after the final examination. By design, an explanation must be provided for all missing data, altered data, and/or out of range data.

The completed case report form must be reviewed and signed by the Investigator named in the study protocol or by a designated sub investigator.

Final monitored and audited CRFs will be provided to the sites at the end of the study in the format of a PDF file.

16.3 Confidentiality of Subject Data

The investigator will ensure that the confidentiality of the subjects' data will be preserved. In the CRF or any other documents submitted to the sponsor, the subjects will not be identified by their names, but by an identification system, which consists of their initials and number in the study. The investigator will maintain documents not meant for submission to the sponsor, e.g., the confidential subject identification code and the signed informed consent forms, in strict confidence.

17. Statistical Methods and Determination of Sample Size

17.1 Determination of Sample Size

The target enrollment of 60 subjects will provide sufficient power while also accounting for potential retention issues. With recruitment of only 44 subjects, we will reach a power of .80. This gives room for some attrition, although we think it will not be more than 5%.

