The sample size is calculated in 3:1 ratio to FGF-2 treatment group or placebo to provide more than 90% power to detect a clinical significant difference at a two-sided significance level of 0.05 using a Fisher's exact test. To allow for 5% dropouts, 45 patients of FGF-2 treatment group and 15 patients of placebo are required.

Data after discontinuations for any reason will not be imputed through the final schedule visit. This subject will be considered as not-improvement.

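### The sample-size text treats dropouts as subjects removed from N, but the synopsis scores them as failures; under that rule power above 90% is not assured and the 44-subject reserve is overstated

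*Combined protocol and SAP*

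**What the plan says.** The Statistical Analysis part of the synopsis claims "more than 90% power to detect a clinical significant difference" "at a two-sided significance level of 0.05 using a Fisher's exact test", with 3:1 allocation. It then gives the numbers: "To allow for 5% dropouts, 45 patients of FGF-2 treatment group and 15 patients of placebo are required". Its next paragraph says that data after discontinuation will not be imputed, and adds: "This subject will be considered as not-improvement".

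Section 17.1 sets a target of 60, states "With recruitment of only 44 subjects, we will reach a power of .80. This gives room for some attrition", and expects attrition of no more than 5%.

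Three other places bear on the point:
- The synopsis also gives 75 as the planned and target enrolment, and section 10.2 describes 75 randomization numbers.
- Section 13.5 requires at least one treatment and a 21-day visit before a subject is evaluated for efficacy.
- Section 17.2 makes the per-protocol set primary for efficacy and excludes important deviations, without saying whether discontinuation is one.

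Neither the synopsis nor section 17.1 gives the two closure rates, the N before inflation, or the inflation formula.

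**The concern.** A dropout can cost power in two ways. If the subject is removed, N falls and the closure rates stay the same. If the subject is kept as a failure, N stays the same but the closure rate in each arm is multiplied by the share who remain, so the difference shrinks too. The sample-size text reasons in the first way and the synopsis's dropout rule works in the second. Power quoted under one rule does not carry over to the other.

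Two statements are at stake: that 45:15 gives more than 90% power after a 5% allowance, and that the gap between 44 and 60 is a cushion against attrition. A team that took the cushion at face value could accept losses believing that power was still .80.

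**Working it through.** **Inputs.** Two-sided Fisher test at 0.05, 3:1 allocation, 45:15 and 5% dropout (synopsis); .80 at 44 and a target of 60 (section 17.1). Assumed, because not stated: that the 44 means 33:11 under the same Fisher test; placebo closure p0 between 5% and 50%; and dropout at random at the same rate d in both arms.

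**Formulas.** Exact power is the sum, over all tables (x, y) that the Fisher test rejects, of Bin(x; n1, p1) × Bin(y; n2, p0). Removal keeps p1 and p0 and lowers n1 and n2. Failure scoring keeps 45:15 and uses (1 − d)p1 and (1 − d)p0.

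**Step 1: the plan's own figures.** The N fits removal: 57 / 0.95 = 60, although no formula is printed. The .80 cannot be reproduced directly without closure rates. The cited human sponge-and-glue study (section 3.2, 98.1% vs 10%) cannot be its basis: those rates give power above 0.9999 at 33:11.

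**Step 2: back-solve.** For each p0, find the p1 that gives exactly 0.80 at 33:11, then evaluate the same pair at 45:15.

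| Placebo p0 | FGF-2 p1 | No dropout, 45:15 | 5% as failures, 45:15 | 5% removed, 43:14 | 16 of 60 as failures | Attrition that keeps .80 |
|---|---|---|---|---|---|---|
| 5% | 47.5% | 0.929 | 0.908 | 0.888 | 0.736 | 21.1% |
| 10% | 55.4% | 0.915 | 0.889 | 0.869 | 0.726 | 18.0% |
| 20% | 69.3% | 0.913 | 0.883 | 0.899 | 0.706 | 16.6% |
| 30% | 79.2% | 0.916 | 0.873 | 0.915 | 0.652 | 12.4% |
| 40% | 86.3% | 0.910 | 0.858 | 0.891 | 0.567 | 9.4% |
| 50% | 92.1% | 0.906 | 0.828 | 0.881 | 0.480 | 6.8% |

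The sixth column multiplies both rates by 44/60 = 0.733; the loss is 16/60 = 26.7%. The last column, also under failure scoring, solves for the d at which 45:15 gives 0.80.

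**Step 3: reading the table.** The two stated powers agree with each other before dropout: rates that give .80 at 44 give 0.906 to 0.929 at 60. With 5% scored as failures, power is below 0.90 at every placebo rate from 10% up, and above .80 everywhere.

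**Step 4: sensitivity.**
- Test: repeating the back-solve with a pooled chi-square approximation gives 0.898 to 0.932 with no dropout, 0.884 to 0.915 with 5% removed, and 0.837 to 0.905 with 5% as failures. The last is again below 0.90 from a placebo rate of 10% up.
- Calibration: if the rates are instead chosen so that 43:14 gives exactly 0.90, failure scoring at 45:15 gives 0.919, 0.915, 0.884, 0.856, 0.869 and 0.846 for placebo rates of 5% to 50%. The shortfall then starts at 20%.
- Rounding: 57 subjects split as 42:15 instead of 43:14 give 0.903 instead of 0.869 at a 10% placebo rate.
- Dropout model: if every dropout would have been a non-closer anyway, nothing is lost and the no-dropout column applies.
- N = 75: at 56:19 with 5% as failures, the Step 2 rates give 0.958, 0.943, 0.949, 0.943, 0.932 and 0.916.

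**The case against.** The strongest reply is that nothing can be shown to fail, because the design rates are not stated. Section 17.1 names neither the test nor the split for the 44, and even 33:11 with Fisher leaves the placebo rate free. At the published 98.1% vs 10%, power at 45:15 is above 0.999 with 5% failures and 0.9987 with 16 of 60 as failures. This stands as a limit on the claim. It does not rescue the text: at those rates the .80 at 44 is itself far off, so section 17.1 needs correcting either way.

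Four stronger readings are tempting, and the documents do not support them.
- A reader might infer that the trial fails to deliver its power. At the plan's own 5% attrition, power stays above .80 in every scenario. More than 90% also survives at a 5% placebo rate (0.908) and at N = 75.
- A reader might infer that the plan permits losing 16 subjects. Section 17.1 speaks of some attrition and expects no more than 5%; it never sets 44 completers as a floor.
- A reader might blame failure scoring alone. Removal at 43:14 also misses 0.90 in five of the six rows, and at placebo rates of 5% and 10% it gives lower power than failure scoring. At those two rates the comparison turns on how 57 subjects are split.
- A reader might infer that every dropout counts as a failure. Section 13.5 can leave out subjects with no 21-day visit, and section 17.2 can remove important deviators. The synopsis rule clearly reaches those who discontinue after the first follow-up; for the others the plan is unsettled.

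**Conclusion.** The concern holds in limited form. The power claim and the attrition allowance use removal arithmetic that does not match the dropout rule in the synopsis. At the effect that section 17.1 implies, more than 90% power at 45:15 is not assured: with 5% random dropouts scored as failures it is about 0.91 falling to 0.83 as the placebo rate rises from 5% to 50%. Under that rule 44 completers out of 60 would not keep .80 (0.48 to 0.74). The attrition that does keep it is about 7% to 21%, less than the 27% that a move from 60 to 44 would represent but more than the 5% expected.

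These sizes rest on the 33:11 Fisher reading, the assumed placebo rates, and equal random dropout in both arms. They describe N = 60 only.

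**What to change.** In section 17.1 and the synopsis:
1. State the two closure rates behind the power claims, the test, and the inflation formula.
2. Settle which dropout rule and analysis set govern the primary test: not improved (synopsis), or removal under sections 13.5 and 17.2.
3. Reconcile the 60 and 75 targets, including section 10.2, where 15 sets of 4 make 60 numbers but 75 are stated.
4. Restate power at the chosen N under the chosen rule.
5. Delete the sentence that 44 subjects leave room for attrition, or replace it with the attrition that the chosen rule tolerates at the stated rates.

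None of the powers or attrition limits above should be copied into the protocol as fixed values, because they depend on assumed placebo rates. A range should not be bounded by the 41% control rate in section 3.1, which comes from chinchillas.

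The cost is wording, and possibly a slightly less favourable stated power. No extra subjects are needed.
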